Patients determined to be eligible for the study by the patient's clinical provider (and per our previously defined criteria) will be recruited to enroll in the project within the first 24 hours of their hospital admission (i.e. 24 hours following the documented H&P Note). They will be offered the opportunity to consent to enrollment in the study and will be assigned by the study team into either the intervention (RibFx belt +current standard of care) (n=35 subjects) or control (current standard of care) arm (n=15 subjects) in a quasi-experimental prospective design: untreated control group with dependent pretest and posttest samples. In this manner, the intervention arm will be both compared to themselves (pretest vs. posttests) as well as to a control group not exposed to the intervention.

Patients upon enrollment in the study will undergo an initial assessment that will include their baseline pain scores, narcotic

consumption, incentive spirometry scores, and the subjective self-reported results of their questionnaire (the pre-test questionnaire- see attached). Patients will continue to be scored on objective (incentive spirometry results, opioid pain medicine consumption) and subjective variables (pain scores) during their hospital course. Between 24-48 hours after enrollment, they will be prompted to again complete a similar 2nd questionnaire post-test (if they are discharged from the hospital at this point in the time course, they will be sent home with the questionnaire and prompted to complete it at home, or asked for an agreed upon time and day for study staff to call the patient to complete the questionnaire over the phone). At their follow up appointment in trauma clinic (which will be coordinated by the research team to be as close as possible to 3 weeks post injury), they will have the opportunity to again voluntarily complete a final short questionnaires (post-test) that assess their pain control and respiratory function over the last 3 weeks. If the patient does not plan to follow up in trauma clinic (or is not asked to), we will ask the patient for an agreeable time and day to call the patient and administer the questionnaire over the phone. At this point, their involvement in the trial will be complete.

All aspects of data collection will be performed only by approved members of Key Personnel.

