All patients will undergo initial "Pre-test" testing which will include baseline pain scores (1-10 traditional pain scale), initial narcotic consumption (in MME) for first 24 hours of hospitalization, maximum incentive spirometry score for first 24 hours of hospitalization, and pre-test questionnaire result (see attached questionnaire #1). As the study continues their relevant data will be collected, including both objective (incentive spirometry scores, opioid pain medication consumption, incidence of atelectasis and pneumonia) and subjective (pain scores, survey result) clinical data. Concurrently, we will complete the trial with the intervention (RibFx belt) phase in which participants will be enrolled in the interventional arm of the study. The objective and subjective data will be collected in an identical fashion- the only difference between groups will be that this group will have been fitted with the RibFx belt for their hospital course and discharge.

The participants (both in the control and interventional groups) will again be asked to complete essentially the same brief surveys in a post-test fashion at two set time points: between 24-48 hours after initial enrollment in the study (Questionnaire #2)(if patient has been discharged at this point, they will be sent home with this survey and instructed when to complete, or facilitated completion by calling the patient at this time), and at 3 weeks post-injury (this will be done at their clinic visit, assuming they are not still admitted to the hospital at this time point).

Patients will also be sent home with a work-book to record their incentive spirometry scores and pain scores (all patients will be sent home with an incentive spirometer, and all patients in the interventional group will be sent home with their Ribfx belt).

[figure not shown]

The following schematic will be used for enrollment group assignment in the study (n=50 total participants):

During the chart review portion of the study, patients who have authorized to have their medical records reviewed will have their post-traumatic records reviewed for the following diagnoses or conditions: respiratory failure, tracheostomy requirement, pneumonia, tube thoracostomy (chest tube), epidural use, intubation rates, hospital length of stay, and mortality.

[figure not shown]
The following schematic represents the patient/subject trial course:

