Each patient in the interventional arm will be fitted with a RibFx orthosis belt, which is to be worn during the majority of their day (excluding showering/bathing). It will be encouraged (though not mandatory) to wear at night. Patients in both the control and interventional arm will be expected to participate in pulmonary hygiene / toilet exercises with guided and independent incentive spirometry as per our normal routine and standard of care. There are no other interventions or procedures that the patients will be subjected to for the research trial- other procedures/interventions will be performed only if the clinical care team feels they are indicated.

For research involving survey, questionnaires, etc.: *Describe the setting and the mode of administering the instrument and the provisions for maintaining privacy and confidentiality. Include the duration, intervals of administration, and overall length of participation. (describe and attach all instruments)*

Not applicable

Patients will be assessed with three short questionnaires in a pretest , posttest fashion at both the onset of the study, 24-48 hours after enrollment, and at their follow-up appointment 3 weeks after (2 post test questionnaires). The initial evaluation will occur on initial assessment prior to placement of the rib belt (or, for the control/ non-intervention group, at the onset/first 24 hours of the study).

Each of the questionnaires is essentially the same with only brief modifications made in the first two questions to make them appropriate for the timing during the clinical course. However these are all attached (see Questionnaire 1,2, and 3). Questionnaires 2 and 3 may be facilitated over the phone if the patient is discharged before the defined time frames are met.

Patients in both the intervention and control arms will present in post-admission follow up at a time period of 3 weeks post injury (range, 2-4 weeks) following their hospital admission, and will be asked to fill out a brief survey regarding their respiratory function and pain control. This survey will also inquire into compliance with the use of incentive spirometer, and compliance with the use of the RibFx belt (for patients in the intervention arm). If patients are not asked to present to trauma clinic for follow up, or if a patient does not intend to follow up, we will aim to complete this questionnaire over the phone in the same time frame.

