Payment for participation: Describe all plans to pay subjects, either in cash, a gift or gift certificate. Please note that all payments must be prorated throughout the life of the study. The IRB will not approve a study where there is only a lump sum payment at the end of the study because this can be considered coercive. The amount of payment must be justified. Clarify if subjects will be reimbursed for travel or other expenses.

Not applicable

There will be no payment or financial incentive for the subjects to participate. The medical device RibFx belt will be provided to the intervention group free of charge, and they will be allowed to keep the medical device upon discharge (MSRP \$125 USD).

Collaborating Sites. When research involving human subjects will take place at collaborating sites or other performance sites when UVM/UVM Medical Center is the lead site, the principal investigator must provide in this section a list of the collaborating sites and their Federalwide Assurance numbers when applicable. (agreements may be necessary)

Not applicable

Single center study at the University of Vermont Medical Center main campus (Burlington, VT). No collaborating centers or satellite/off-site locations.

INFORMED CONSENT

Consent Procedures: Describe the consent procedures to be followed, including the circumstances under which consent will be obtained, who will seek it, and the methods of documenting consent. Specify the form(s) that will be used e.g. consent (if multiple forms explain and place identifier on each form), assent form and/or HIPAA authorization (if PHI is included). These form(s) must accompany the protocol as an appendix or attachment.

Note: Only those individuals authorized to solicit consent may sign the consent form confirming that the prospective subject was provided the necessary information and that any questions asked were answered.

Consent will be obtained at the time of enrollment (during the first 24 hours of the patient's inpatient admission/observation, on their initial encounter for acute traumatic rib fracture) and consent will be obtained at the bedside by one of the members of the research team.

All documentation of consent observation/supervision will be kept in the study regulatory binder.

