After verbally explaining the rational, reasoning, risks, and potential benefits of the study, patients will have ample opportunity to decide whether or not to enroll without feeling pressured into enrolling (up to 24 hours will be permitted for deciding). Relevant written materials will be left for further review, including a written consent form, device pamphlet, and information pamphlet (All included in the IRB materials). Upon request of the patient, a member of the research team will always be available to answer further questions regarding the study via a "hot line" and also via the clinical care team.

Information Withheld From Subjects: Will any information about the research purpose and design be withheld from potential or participating subjects? If so, explain and justify the non-disclosure and describe plans for post-study debriefing.

Not applicable

No information will be withheld from subjects. N/A

Attach full grant application, including budget information and/or any contract or draft contract associated with this application.

All materials must be submitted electronically to the IRB via InfoEd. Proper security access is needed to make electronic submissions. Visit the [InfoEd Resource Materials](#) page for more information.

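### The baseline opioid total and maximum spirometry run over hospital hours 0 to 24, enrolment falls inside those hours, and nothing keeps belt time out of the baseline

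*Combined protocol and SAP*

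**What the plan says.** The Study Design part of Methods and Procedures lists the pre-test measures. Two of them cover a fixed block of hospital time: "initial narcotic consumption (in MME) for first 24 hours of hospitalization, maximum incentive spirometry score for first 24 hours of hospitalization". The other two, the baseline pain score and the first questionnaire, are point assessments.

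The opening study summary says that patients "will be recruited to enroll in the project within the first 24 hours of their hospital admission", counted from the admission H&P note. Consent Procedures agrees: "Consent will be obtained at the time of enrollment (during the first 24 hours of the patient's inpatient admission/observation". It adds that "up to 24 hours will be permitted for deciding".

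Two places bear on the order of baseline and belt:

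- The study summary ties the baseline to enrolment: "Patients upon enrollment in the study will undergo an initial assessment that will include their baseline pain scores, narcotic" consumption, spirometry and the first questionnaire.
- The section on surveys and questionnaires says: "The initial evaluation will occur on initial assessment prior to placement of the rib belt".

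On wear, Study Design says that "this group will have been fitted with the RibFx belt for their hospital course and discharge". The text gives no hour for fitting.

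The study summary names each patient's own pre-post comparison as the main aim. Under Objectives, narcotic consumption is part of the primary objective and spirometry part of the secondary one.

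**The concern.** A total or maximum over hospital hours 0 to 24 is a pre-belt value only if the belt goes on at hour 24 or later. A patient who enrols at hour 8 has no 24-hour total yet. Either the baseline is completed after fitting, or fitting waits, or the baseline is cut short. The protocol does not say which.

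If the baseline is completed after fitting, the pre value already carries some of the belt's effect, and by an amount that varies with how early the patient is fitted. Two results are then at risk. One is the opioid part of the primary objective. The other is the pulmonary part of the hypothesis, that pain improves at no cost to lung function: a fall in spirometry caused by the belt could look smaller than it is.

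**Working it through.** **The plan's own figure.** Statistical Considerations gives 83% power at n = 30 and 88% at n = 35 for a 20% fall in MPQ PRI, with mean 28, SD 16, within-subject correlation 0.8 and two-sided alpha 0.05.

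- SD of the difference = 16 × √(2 × (1 − 0.8)) = 10.12
- Difference = 0.20 × 28 = 5.6; standardised effect = 5.6 / 10.12 = 0.553
- Paired t-test (noncentral t): 83.4% at n = 30 and 88.9% at n = 35

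The plan's figures are reproduced to within one point. They concern a pain score, not a 24-hour total, so the overlap leaves them unchanged.

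**Timing, side by side.**

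| Item | Stated timing |
|---|---|
| Opioid total and maximum spirometry, pre-test | Hospital hours 0 to 24 |
| Enrolment and consent | Any time within 24 hours of the H&P note |
| Initial assessment | At enrolment |
| Belt fitting | Not stated |
| First post-test questionnaire | 24 to 48 hours after enrolment |

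Waiting until hour 24 to fit the belt would not settle the matter. A patient enrolled at hour 2 could reach the first post-test at hour 2 + 24 = 26, with 26 − 24 = 2 hours of belt wear.

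**Dilution of the opioid effect.** Assumptions, none of them from the documents: a constant underlying opioid rate, an immediate and constant belt effect, a true 20% reduction, a post window wholly on the belt, and the hospital and H&P clocks starting together. With fitting at hour t and the off-belt rate set to 1:

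- Baseline rate = t/24 + 0.8 × (24 − t)/24
- Post rate = 0.8
- Apparent decrease = 1 − 0.8 / baseline rate

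| Fitting hour t | Baseline rate | Apparent decrease | Share of the absolute effect kept |
|---|---|---|---|
| 24 | 1.00 | 20% | 100% |
| 18 | 0.75 + 0.20 = 0.95 | 15.8% | 0.15 / 0.20 = 75% |
| 12 | 0.50 + 0.40 = 0.90 | 11.1% | 0.10 / 0.20 = 50% |
| 6 | 0.25 + 0.60 = 0.85 | 5.9% | 0.05 / 0.20 = 25% |

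Control baselines contain no belt time. If recovery adds the same amount R to both arms, the true belt effect is B and the on-belt share of the window is f, the belt arm changes by R + (1 − f)B and the controls by R. The contrast is (1 − f)B, so it is diluted as well.

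**Spirometry.** A maximum does not dilute in proportion. In an illustrative simulation (assumed: 12 readings per window, within-patient SD 150 ml, a belt shift of 150 ml), the share of the shift still visible was:

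| On-belt share of the baseline window | Belt raises spirometry | Belt lowers spirometry |
|---|---|---|
| 0.25 | 56% | 87% |
| 0.50 | 30% | 70% |
| 0.75 | 13% | 44% |

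Both directions are muted, including harm. The percentages depend on the assumed inputs.

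**The case against.** The best defence is that contamination is nowhere documented. No fitting time is stated, the patient-course schematic is missing from the text reviewed, and patients may take up to 24 hours to decide, so some may have little or no overlap. The summary places the narcotic and spirometry baseline at enrolment, which allows a reading in which only values available before the belt are used. This stands: the documents support saying that the baseline may contain belt time, not that it does. It does not remove the conflict, because Study Design still prescribes the full 24 hours.

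The sentence placing the evaluation before the belt appears among the questionnaire procedures and may cover Questionnaire 1 only. It conflicts with the 24-hour window only if it also covers opioid use and spirometry. The conflict with the enrolment assessment in the summary does not depend on it.

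A reader might infer that the measured pre-post change must understate the belt effect. The documents do not support that. Statistical Considerations expects pain to improve with time whatever the treatment, so the total change also contains recovery and may still overstate the belt effect. Only the belt component is diluted.

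A reader might also carry the plan's 88% power over to opioid use and quote a loss of power. The plan has no power calculation for opioid use. Its only opioid figure, 135.8 (IQR 50.83 to 440.0), is strongly skewed and gives no basis for borrowing the MPQ PRI standard deviation or correlation. No power figure for opioid use should be quoted.

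Finally, this is a quality-improvement pilot, and the problem touches one of several primary pain measures and one secondary measure. That limits its severity.

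**Conclusion.** The concern holds as an unreconciled definition. As written, the rule admits on-belt time to the baseline opioid total and maximum spirometry of any belt-arm patient fitted before hour 24. Under the stated assumptions, an opioid reduction of 20% would appear as anything from 20% (fitting at hour 24, no dilution) down to 5.9% (hour 6). Where in that range the trial would fall cannot be derived from the documents. For spirometry the direction is toward muting, with no size that can be stated from the plan. The belt-versus-control contrast, which the plan says is not powered, is diluted in the same way for opioid use. Pain scores, Questionnaire 1 and the MPQ PRI power stand. This should be fixed, but it does not invalidate the design.

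**What to change.** Reconcile the study summary, Study Design and the questionnaire section, and define the two baselines as follows:

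1. Record the clock time of belt fitting, or of group assignment for controls, on the case form.
2. End the baseline window for both measures at that time.
3. Express opioid use as MME per hour before and after it, with the post window defined from the same time point.
4. Compare the pre-belt maximum spirometry with the maximum over a post window matched in length or in number of attempts. Without matching, a maximum over a shorter pre-belt window is systematically lower, which could hide a belt-related fall.

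This is a change of measurement definition and leaves care as it is. It costs some protocol wording and one recorded time per patient, and needs opioid doses and spirometry readings with their times. The downside is a shorter, noisier baseline for patients enrolled early. It should be done before enrolment, because without recorded fitting times the overlap may not be recoverable at analysis.

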Secondary objectives: Compare pulmonary hygiene and function amongst patients with non-operatively managed traumatic rib fractures via incentive spirometry scores and incidence of post-traumatic pneumonia and radiological evidence of atelectasis incidence

METHODS AND PROCEDURES

Study Design: *Describe the research design, including a description of any new methodology and its advantage over existing methodologies.*

Per Jeffords Institute for Quality Data, there were 190 patients admitted to the Acute Care Surgery (Trauma) service at the University of Vermont Medical Center during the year 2016. Assuming that these numbers remain fairly static overtime as they have in the past, we would expect approximately 16 patient admissions per month with the diagnosis of rib fracture (seasonal fluctuations do exist with more traumatic admissions during the summer months). The goal time period for the trial would be to conduct this trial during the summer, with a goal of 50 total patients. We would therefore expect an enrollment period (data collection phase) of approximately 3 months.

During the study (following appropriate IRB approval), appropriate patients will be recruited both to the control arm of the study and the intervention/comparison arm in a specified / non-randomized sequence as seen in the schematic below (First 5 patients control, next 5 patients intervention, next 5 patients control, next 5 patients intervention, next 5 patients control, final 25 patients intervention). Control arm will include 15 total patients. All will be consented to the study upon admission (first 24 hours of index hospitalization for injury) with full knowledge that they will either be undergoing no intervention other than receiving the current standard of care for rib fracture care per our institution's standard, and if assigned to the rib belt group, expected to wear the rib belt during their recovery.

The current standard of care for rib fractures at our institution is as follows: includes oral and IV analgesia and other multimodal pain control as appropriate, including muscle relaxants such as methocarbamol (robaxin) unless there is a contraindication, pulmonary hygiene/toilet and respiratory care (including frequent evaluations by physicians, respiratory therapists, and nursing staff, early mobilization, and monitoring for pulmonary complication (via vital signs, pulse oximetry, oxygen requirement, chest imaging if appropriate).

[figure not shown]

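### The chart review does not separate events before belt fitting from later ones, and its visible text sets no end date

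*Combined protocol and SAP*

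**What the plan says.** Under Methods and Procedures, Study Design, the chart-review paragraph states that patients who have authorised access "will have their post-traumatic records reviewed for the following diagnoses or conditions". The items that it then names are "respiratory failure, tracheostomy requirement, pneumonia, tube thoracostomy (chest tube), epidural use, intubation rates, hospital length of stay, and mortality". It does not tie the count to enrolment or to belt fitting, and it gives no closing date.

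Other sections place the belt later than the start of that record:

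- The opening description of the study says that eligible patients "will be recruited to enroll in the project within the first 24 hours of their hospital admission", timed from the H&P note.
- The questionnaire section under Procedures states: "The initial evaluation will occur on initial assessment prior to placement of the rib belt". For controls, the matching point is the start of the study or its first 24 hours.
- Participation ends with the final questionnaire: "At this point, their involvement in the trial will be complete". The follow-up visit for both arms is "at a time period of 3 weeks post injury (range, 2-4 weeks) following their hospital admission".
- Assignment follows a fixed, non-randomised order of blocks that ends "next 5 patients control, final 25 patients intervention".

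The hypothesis (Purpose) and the Objectives both include no increase in respiratory complications. The secondary objective names incentive spirometry, pneumonia and atelectasis. Intubation on arrival or within the first 24 hours is an exclusion criterion. Statistical Considerations lists epidural use among clinical-course variables and states that the study is not powered to compare the arms.

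**The concern.** A chest tube or epidural placed at presentation, or a respiratory diagnosis made in the first hours, cannot have been caused or prevented by a belt fitted afterwards. Read literally, the chart review pools such events with those that follow fitting.

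This has two consequences. First, events that the belt could not influence are added to both arms and dilute any real difference. That matters when the hoped-for conclusion is no increase in complications. Second, because allocation is by enrolment order, severity at presentation need not balance between 15 controls and 35 belt patients. An imbalance that existed before the belt could then be read as benefit or harm.

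The plan also says that the data may inform the power calculation for a definitive randomised trial. Complication rates that include events before enrolment would carry into that design.

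A missing end date raises a separate question, whether every patient is observed for the same length of time.

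**Working it through.** **The plan's only power figure.** It concerns pain, not complications. Inputs from Statistical Considerations: MPQ PRI mean 28, SD 16, a 20% fall (0.20 × 28 = 5.6), within-subject correlation 0.8, two-sided alpha 0.05.

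- SD of change = 16 × √(2 × (1 − 0.8)) = 10.12.
- Non-centrality = (5.6 / 10.12) × √n = 3.03 at n = 30 and 3.27 at n = 35.
- Paired t-test power = 83.4% and 88.9%, against 83% and 88% stated.

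That figure reproduces, and nothing below changes it. The plan gives no figure for complications.

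**Dilution.** The documents give no event rates, so these are assumptions. Let p be the share of both arms with the event before enrolment, and let the risk after fitting be 15% (belt) and 5% (control). Counted risk = p + (1 − p) × risk after fitting.

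| p | Belt | Control | Difference | Ratio |
|---|---|---|---|---|
| 0 | 15.0% | 5.0% | 10 points | 3.00 |
| 0.10 | 0.10 + 0.90 × 0.15 = 23.5% | 0.10 + 0.90 × 0.05 = 14.5% | 9 points | 1.62 |
| 0.20 | 0.20 + 0.80 × 0.15 = 32.0% | 0.20 + 0.80 × 0.05 = 24.0% | 8 points | 1.33 |
| 0.30 | 0.30 + 0.70 × 0.15 = 40.5% | 0.30 + 0.70 × 0.05 = 33.5% | 7 points | 1.21 |

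The ratio falls steeply and the difference only modestly, but the noise rises as well. At p = 0.20:

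- All events counted (35 and 15 patients): SE = √(0.32 × 0.68/35 + 0.24 × 0.76/15) = 0.136; difference/SE = 0.08/0.136 = 0.59.
- Only patients still free of the event at fitting (28 and 12): SE = √(0.15 × 0.85/28 + 0.05 × 0.95/12) = 0.092; difference/SE = 0.10/0.092 = 1.08.

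**Imbalance at presentation.** One extra event before the belt moves the control rate by 1/15 = 6.7 points and the belt rate by 1/35 = 2.9 points. Two extra among controls move their rate by 13.3 points, more than the whole 10-point difference assumed above.

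**End of the review.** From the stated order, controls hold positions 1–5, 11–15 and 21–25. These sum to 195, mean 195/15 = 13.0. Belt positions sum to 1275 − 195 = 1080, mean 1080/35 = 30.9. The gap is 17.9 positions.

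- At 190 admissions a year: 17.86 × 365/190 = 34.3 days. At 16 a month it is 34.0 days, and at 50 patients in 3 months it is 32.6 days. At half the 16-a-month rate it would double to about 68 days.
- If all charts were read to one date 21 days after the last enrolment (16 a month), mean observation would be 91 days in controls and 57 in belt patients, a ratio of 1.59.
- The effect on events depends on when they occur. Assume exponential onset, the same reading date and 16.7 patients a month. A mean onset of 7 days gives capture of 100% of control and 99% of belt events. A mean onset of 21 days gives 98% and 88%.
- If each chart is instead read to a fixed 3 weeks per patient, the planned difference is 0 days.

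**The case against.** The strongest reply is that the plan does not call these items outcomes. Chest tube and epidural appear in no objective, Statistical Considerations treats epidural use as a clinical-course variable, and a blinded radiologist grades presenting pneumothorax and pleural fluid as baseline severity. Early intubation is already excluded. The comparison between arms is declared unpowered: a 5% risk in 15 controls is 0.75 expected events.

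Much of this stands. A reader might infer that early chest tubes and epidurals carry the claim of no added respiratory complications; the Objectives do not support that. The gap remains because the chart review lists these items alongside respiratory failure, pneumonia and mortality without dividing baseline from outcome. Pneumonia, a named secondary endpoint, has no onset rule either. Grading the initial imaging does not date a procedure or a diagnosis.

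A reader might also infer that early controls are in fact observed longer, which would make the belt look safer or riskier than it is. The documents do not support that. It requires one calendar cut-off for all charts, and none is stated. The end of involvement at about 3 weeks in both arms, with data collected the same way in each, points to an end set per patient, although the plan does not expressly apply it to the chart review. The trial-course and timeline figures are not available here and may show the timing.

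Finally, events before the belt are gathered alike in both arms, so in themselves they dilute the comparison and do not favour either arm.

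**Conclusion.** The point holds for the start of counting. The chart review draws on a record that opens at injury, the belt comes later, and nothing in the text separates events before fitting from those after it. On the assumed rates, the difference falls from 10 points to between 9 and 7 as the share with an earlier event rises from 10% to 30%, and the ratio falls from 3.0 to between 1.62 and 1.21. The sizes rest on assumed rates; that a real difference is diluted does not. A presentation imbalance of one or two patients among 15 controls could matter as much as the dilution.

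For the end of counting, the finding is only that the visible text gives none. The 34-day gap is conditional on a single reading date that the documents do not contain.

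The consequence is limited to the complication part of the hypothesis and to any rates passed on to a later trial. The within-patient pain comparison is untouched.

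**What to change.** Add one rule to the chart-review paragraph and repeat it in Statistical Considerations:

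- Extract an onset date, and a time on the day of fitting, for each chart-review event.
- Count an event as an outcome only if its onset is after belt fitting (after the pre-test in controls) and on or before one fixed day that is the same for every patient, for example day 21 after enrolment. The date of the follow-up contact should not close the window, because that contact may fall anywhere from 2 to 4 weeks and windows would then differ by up to two weeks.
- Report earlier events by arm as baseline characteristics.
- State whether a patient with an earlier event of the same type stays in the denominator. The precision calculation above leaves such patients out.

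The cost is one date field per event in an extraction that is already manual, and slightly fewer counted events. Sample size, visits and the pain analysis do not change.
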